**3.3.16. Serum concentrations of GDF-15 on CCI**  
(Cohort B only)

See Section 3.3.10.

**3.3.17. Incidence of ADA, and NAb (Cohort B only)**

See Section 3.3.11.

**3.3.18. Fold change from baseline in NT-proBNP at Weeks 12 and 16 (Cohort B only)**

See Section 3.3.12.

**3.4. Baseline Variables**

Modified BMI (mBMI) will be calculated at baseline as:

$$\frac{\text{weight at Day 1 [kg]}}{\text{height at screening [m]}^2} \times \text{serum albumin at Day 1 [g/L]}$$

**3.5. Safety Endpoints**

The change from baseline for ECGs (heart rate, QT, QTcF, PR and QRS interval) will be calculated for all post baseline timepoints. The maximum increase from baseline over all measurements taken post-dose will be calculated for QTcF. The maximum increase from baseline will be calculated as the maximum change from baseline for a participant, except in the case where a participant does not show an increase. In such an instance, the minimum decrease should be taken.

Other safety endpoints are covered in Section 3.2.5.

**4. ANALYSIS SETS (POPULATIONS FOR ANALYSIS)**

Participant Analysis Set	Description
Enrolled/Randomly assigned to study intervention	"Enrolled" means a participant's agreement to participate in a clinical study following completion of the informed consent process and randomization. A participant will be considered enrolled if the informed consent is not withdrawn prior to participating in any study activity after screening. Potential participants who are screened for the purpose of determining eligibility for the study, but do not participate in the study, are not considered enrolled, unless otherwise specified by the protocol.
Evaluable	All participants randomly assigned to study intervention and who take at least 1 dose of study intervention (not including the open-label placebo administered in screening), for the given part of the study (Main Cohort [Cohort A], open-label, PK cohort [Cohort B], Cohort C or Cohort D). Participants will be analyzed according to the randomized intervention.
Safety Analysis Set	All participants randomly assigned to study intervention and who take at least 1 dose of study intervention (not including

	
the open-label placebo administered in screening), for the given part of the study (Main Cohort [Cohort A], open-label, PK cohort [Cohort B], Cohort C or Cohort D). Participants will be analyzed according to the product they actually received. This will be the study intervention received by the participant for the majority of the timepoints during the study (not including the open-label placebo administered in screening). If a participant receives an equal number of different doses, then the lowest of those doses will be used. If a participant receives an equal number of placebo and a given dose of ponesegromab, the ponesegromab dose will be used.

--	--

Defined Analysis Set	Description
Censored	All evaluable participants. For participants who discontinue study intervention or receive a prohibited procedure, all observations post-discontinuation (i.e. last dose of IP +31 days), or post-procedure, will be censored and treated as missing data. For participants who miss a dose, or receive an incomplete dose, all observations post-missed/incomplete dose will be censored. For participants who resume dosing, their subsequent data may be included in the analysis following a review of their compliance prior to database lock.
Complete	All evaluable participants. For participants who discontinue study intervention, receive a prohibited procedure and/or miss a dose, or receive an incomplete dose, all observations post-discontinuation, post-procedure or post-missed/incomplete dose will be included in the analysis set.
PK concentration	All participants randomly assigned to study intervention and who take at least 1 dose of ponesegromab and in whom at least 1 PK concentration value is reported, for the given part of the study (Main Cohort [Cohort A], or open-label, PK cohort [Cohort B], Cohort C or Cohort D).
PK parameter (Cohort B only)	All participants randomly assigned to study intervention and who take at least 1 dose of ponesegromab and have at least 1 of the PK parameters of interest calculated.
PD	All participants randomly assigned to study intervention and who take at least 1 dose of study intervention and in whom at least 1 PD (GDF-15 CCI ) concentration

	value is reported, for any PD endpoint, for the given part of the study (Main Cohort [Cohort A], or open-label, PK cohort [Cohort B], Cohort C or Cohort D).
Immunogenicity	All participants randomly assigned to study intervention and who take at least 1 dose of ponesegromab and in whom at least 1 ADA result is reported, for the given part of the study (Main Cohort [Cohort A], or open-label, PK cohort [Cohort B], Cohort C or Cohort D).

#### 4.1. Prohibited Procedures

Listings of non-drug treatment(s)/procedure(s) will be provided (see Section 6.5.5). These will be blinded tables and will be reviewed prior to database lock to determine which procedures would be classed as “prohibited”.

#### 4.2. Treatment Compliance

Treatment dosing will be reviewed prior to database lock to determine, for participants who miss a dose, or receive an incomplete dose, and resume (complete) dosing, whether their subsequent data may be included in the analysis. Subsequent data will be included immediately after (complete) IP dosing is resumed.

#### 4.3. Incorrect Randomization

Participants who are randomized to the wrong stratum, in error, will have the incorrect stratum assignment remain in IMPALA but the clinical database will include the correct stratum. The latter will subsequently be used for all relevant analyses, if appropriate.

### 5. GENERAL METHODOLOGY AND CONVENTIONS

#### 5.1. Hypotheses and Decision Rules

Primary statistical inference will be based on the primary endpoint, change from baseline in KCCQ-23 CSS at Week 22. *The null hypothesis of no difference between ponesegromab and placebo will be tested for the 300 mg dose group from Cohort A only. The alternative hypothesis is that ponesegromab is superior to placebo.* The Type I error rate ( $\alpha$ -level) used for the statistical inference will be 5% (1-sided). Each dose of ponesegromab will be compared separately with placebo. No adjustment for multiple comparisons will be made.

Similar hypotheses will be applied to the secondary efficacy endpoints (and selected exploratory efficacy endpoints), where the type I error rate will also be 5% (1-sided). Note the alternative hypothesis for the response endpoint is that ponesegromab is superior to placebo as shown by an odds ratio  $> 1$ . Note also that these additional inferences for the 300 mg ponesegromab treatment group will also be based on data from Cohort A only. Inference for the 100 and 200 mg ponesegromab treatment groups will be based on data from Cohorts A and C combined.

For all other endpoints, the results of any statistical analyses are for exploratory purposes only and there is no formal hypothesis testing.

*There is no hypothesis testing planned for the open-label, PK cohort.*

## 5.2. General Methods

*Following PCD, the data will be analyzed and reported in a CSR. The results for the open-label, PK cohort (Cohort B) may be reported in a separate CSR.*

*For safety analyses and PK/PD/immunogenicity analyses, the Main Cohort (Cohort A) and Cohort C will be reported combined, with data from the same treatment group combined across cohorts; the open-label, PK cohort (Cohort B) will be reported separately; Cohort D will be reported separately.*

Efficacy analyses will be produced using 4 different approaches:

1. Main Cohort (Cohort A) only: The main efficacy analyses for the 300 mg ponesegromab treatment group will be performed using data from the Main Cohort (Cohort A) only; statistical models will include data from the 300 mg ponesegromab treatment group and placebo only. Summaries will include data from all treatment groups.
2. The open-label, PK cohort (Cohort B) only: The open-label, PK cohort (Cohort B) will be presented separately from the Main Cohort (Cohort A), Cohort C and Cohort D.
3. Main Cohort (Cohort A) and Cohort C combined: The main statistical analyses for the 100 mg and 200 mg ponesegromab treatment groups will be performed using combined data from the Main Cohort (Cohort A) and Cohort C; statistical models will include data from all three ponesegromab treatment groups and placebo, with these analyses also providing sensitivity analyses for the 300 mg ponesegromab treatment group. Summaries will include data from all treatment groups. Data from the same treatment group will be combined across cohorts, and cohort will be added as a term in the statistical models.
4. Main Cohort (Cohort A) and Cohort D combined: These analyses will provide sensitivity analyses for the 300 mg ponesegromab treatment group, in participants with any serum GDF-15 concentration. Both summaries and statistical models will include data from the 300 mg ponesegromab treatment group and placebo only. Data from the same treatment group will be combined across cohorts, and cohort will be added as a term in the statistical models.

The analyses related to the primary, secondary and exploratory endpoints will be based on the appropriate population for analysis (see Section 4).

Unless otherwise stated, all summaries and plots will be presented by treatment group. The following treatment group labels (or similar) will be used:

DMB02-GSOP-RF02 7.0 Statistical Analysis Plan Template 31-Jan-2022

PFIZER CONFIDENTIAL

TMF Doc ID: 98.03

Page 32 of 85

Placebo  
Ponsegromab 100 mg  
Ponsegromab 200 mg  
Ponsegromab 300 mg

A ponsegromab combined treatment group (combined over the ponsegromab doses, either within a single cohort or within combined cohorts) and an overall treatment group will also be presented for safety analyses.

### 5.2.1. Summaries for Continuous Endpoints

Unless otherwise stated, continuous variables will be presented using summary statistics: number of observations, arithmetic mean, standard deviation (SD), median, 25th and 75th percentiles, and range (minimum and maximum) values. For endpoints to be analyzed on the natural log scale ( $\log_e$ ), the geometric mean and geometric coefficient of variation (CV) will additionally be presented.

### 5.2.2. Summaries for Categorical Endpoints

Categorical variables will be presented using summary statistics: number of observations and percentages.

### 5.2.3. Mixed Models Repeated Measures (MMRM) Analysis

*The MMRM model will include participant as a random term, and baseline, time (as a factor), baseline-by-time interaction, treatment and treatment-by-time interaction as fixed terms in the model. An unstructured covariance matrix will be fitted to the repeated times within subject (other covariance matrices will be considered if necessary), and the Kenward-Roger approximation will be used for estimating degrees of freedom. Additional terms may be fitted in the model (eg, cohort, baseline LVEF, log GDF-15 concentration from SV1, baseline log NT-proBNP), as appropriate. Least squares means (and 90% CIs) and mean differences versus placebo (and 90% CIs and p-values, for primary, secondary, and selected exploratory endpoints) will be provided. No adjustments will be made for multiplicity. In addition, the following plots will be produced:*

- Profile plots of the LS means (and 90% CIs) over time, with a separate line for each treatment group
- Profile plots of the LS mean differences to placebo (and 90% CIs) over time, with a separate line for each dose of ponsegromab.

Standard SAS output will be provided to support the statistical summary table for the analysis model, but will not be included in the CSR.

Example SAS code is provided in Appendix 4.

### Statistical Model Diagnostics

The presence of outliers will be investigated for this model. An outlier will be defined as any response data value with a studentized (conditional) residual greater than 3, or less than -3. A listing will be presented of any participants meeting these criteria and will be included with standard SAS output. The assumptions of normality will be verified graphically using residual plots. For each fitted model, a set of conditional studentized residual plots will be produced, including residual plot, histogram of normality, quantile-quantile (QQ) plot and summary of fit statistics. The residual plots will not be included in the CSR.

If there are outliers or major deviations from normality, then the effect of these on the conclusions may be investigated through alternative transformations and/or analyses excluding outliers. Justification for any alternative to the planned analysis will be given in the report of the study.

#### **5.2.4. Logistic Regression with multiple imputation**

*The logistic regression model will include baseline score and treatment as fixed terms in the model. Additional terms may be fitted in the model (eg, cohort, baseline LVEF, log GDF-15 concentration from SV1, baseline log NT-proBNP), as appropriate. Missing values (e.g. due to censoring) will be imputed for missing data using a multiple imputation method as described in Section 5.3. Odds (and 90% CIs) and odds ratios versus placebo (and 90% CIs [and p-values, for secondary endpoints]) will be provided. No adjustments will be made for multiplicity.*

Standard SAS output will be provided to support the statistical summary table for the analysis model and multiple imputation approach, but will not be included in the CSR.

Example SAS code is provided in Appendix 4.

#### **5.2.5. Analysis of Covariance (ANCOVA)**

The ANCOVA model will include baseline and treatment as fixed terms in the model. Additional terms may be fitted in the model (eg, cohort, baseline LVEF, log GDF-15 concentration from SV1, baseline log NT-proBNP), as appropriate. Least squares means (and 90% CIs) and mean differences versus placebo (and 90% CIs) will be provided. No adjustments will be made for multiplicity. In addition, plots of LS means and differences (including 90% CIs for both) will be produced.

Standard SAS output will be provided to support the statistical summary table for the analysis model, but will not be included in the CSR.

Example SAS code is provided in Appendix 4.

### Statistical Model Diagnostics

The presence of outliers will be investigated for this model. An outlier will be defined as any response data value with a studentized (conditional) residual greater than 3, or less than -3. A

listing will be presented of any participants meeting these criteria and will be included with standard SAS output. The assumptions of normality will be verified graphically using residual plots. For each fitted model, a set of conditional studentized residual plots will be produced, including residual plot, histogram of normality, quantile-quantile (QQ) plot and summary of fit statistics. The residual plots will not be included in the CSR.

If there are outliers or major deviations from normality, then the effect of these on the conclusions may be investigated through alternative transformations and/or analyses excluding outliers. Justification for any alternative to the planned analysis will be given in the report of the study.

#### **5.2.6. Logistic Regression without multiple imputation**

The logistic regression model will include treatment as a fixed term in the model. Additional terms may be fitted in the model (eg, cohort, baseline LVEF, log GDF-15 concentration from SV1, baseline log NT-proBNP), as appropriate. Missing values (e.g. due to censoring) will not be imputed. Odds (and 90% CIs) and odds ratios versus placebo (and 90% CIs [and p-values, for selected endpoints]) will be provided. No adjustments will be made for multiplicity.

Standard SAS output will be provided to support the statistical summary table for the analysis model, but will not be included in the CSR.

Example SAS code is provided in Appendix 4.

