9.5. Sample Size Determination

The planned total sample size for the study is up to approximately 781 randomized participants.

Main Cohort (Cohort A)

A sufficient number of participants will be screened to achieve a total of approximately 416 randomized participants, with 380 participants randomly assigned to ponsegromab 300 mg Q4W and placebo Q4W in approximately a 1:1 ratio, plus an additional 36 participants randomly assigned to ponsegromab 100 mg Q4W and 200 mg Q4W in approximately a 1:1 ratio. Participants will be randomized initially in a 1:1:1:1 ratio to all four treatment arms (until approximately 72 participants are randomized), followed by a 1:1 ratio to the 300 mg Q4W and placebo arms only. This planned number of randomized participants is expected to ensure completion of the Main Cohort (Cohort A) of approximately 161 evaluable participants in the 300 mg Q4W and placebo Q4W treatment arms and approximately 15 evaluable participants in the 100 mg and 200 mg Q4W treatment arms, assuming a discontinuation rate of 15% (if this rate is higher, or there is a high rate of non-compliance, more participants may be randomized to ensure the required number of evaluable participants).

The sample size in the ponsegromab 300 mg Q4W and placebo arms is based

CCI

CCI

The sample size in the ponsegromab 100 mg and 200 mg Q4W arms has been chosen empirically to provide sufficient data to gain a preliminary understanding of the PK/PD relationship in this population, and is not based on the primary endpoint.

Open-Label, PK Cohort (Cohort B)

Approximately 20 additional participants will be randomly assigned to open-label ponsegromab 100 mg, 200 mg and 300 mg Q4W in approximately a 1:2:2 ratio. This sample size has been chosen empirically to provide sufficient evaluable participants (approximately 15) to adequately evaluate the PK of ponsegromab following repeated SC administration to participants with HF and elevated circulating GDF-15 concentrations, assuming a 15% discontinuation rate (if this rate is higher, or there is a high rate of non-compliance, more participants may be randomized to ensure the required number of evaluable participants).

Cohort C (optional)

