### 3.3.14. Clinical outcomes (Cohorts A, C and D)

Both investigator-reported and adjudicated events will be recorded.

#### 3.3.14.1. Hierarchical composite endpoint of time to cardiovascular death, number of worsening HF events (hospitalization for HF, or urgent HF visit), time to first worsening HF event and change from baseline in KCCQ-23 CSS at Week 22

The time (days) to cardiovascular death will be calculated for each participant.

The number of hospitalizations for HF and the number of urgent HF visits, over the 22 weeks, will be calculated for each participant. The total number of these worsening heart failure events will also be calculated for each participant, as well as the total number divided by the number of days of study participation (up to Week 22), where 'number of days of study participation' = time from randomization to Week 22, or to time lost-to-follow-up, withdrawal from study, or death. This total will then be multiplied by 154 days in order to provide a 22-week estimate. Similarly, the total number of combined cardiovascular deaths and worsening heart failure events will be calculated.

The composite HF outcome (cardiovascular death, hospitalization for HF or urgent HF visits) will be determined for each participant as well as each individual component as a first event.

The time (days) to first hospitalization for HF and the time (days) to first urgent HF visit will be calculated for each participant. The time to the first of these worsening HF events (hospitalization for HF or urgent HF visit) will also be calculated for each participant.

The change from baseline in KCCQ-23 CSS at Week 22 will be calculated (see Section 3.1.1).

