### 6.3. Other Endpoint(s)

Unless otherwise stated these analyses will be performed on the censored analysis sets, as defined in Section 4, using efficacy approaches 1, 3 and 4, as described in Section 5.2, unless otherwise stated.

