**6.3.14. Clinical outcomes (Cohorts A, C and D)**

The following sections are applied to adjudicated clinical outcome events. Summaries and analyses will use efficacy approaches 1, 3 and 4 for all endpoints, as described in Section 5.2.

**6.3.14.1. Hierarchical composite endpoint of time to cardiovascular death, number of worsening HF events (hospitalization for HF, or urgent HF visit), time to first worsening HF event and change from baseline in KCCQ-23 CSS at Week 22**

The hierarchical composite will be analyzed using the unmatched, win-ratio approach, as described in Section 5.2.9.

Additionally, the number of participants with the composite HF outcome (cardiovascular death, hospitalization for HF or urgent HF visits), and the number of participants with each individual component as their first event, will be summarized descriptively by treatment group, as described in Section 5.2.2. The presentation will also include the total number of combined cardiovascular deaths and worsening HF events (HF hospitalizations and urgent HF visits), including the total number of each component, summarized descriptively by treatment group, as described in Section 5.2.2.

The number of participants with the composite HF outcome (cardiovascular death, hospitalization for HF or urgent HF visits) over 22 weeks will also be analyzed using a logistic regression model (as described in Section 5.2.6), without any multiple imputation.

**6.3.14.2. Time to first occurrence of the clinical composite of cardiovascular death, hospitalization for HF, or urgent HF visit**

Time to first occurrence of the clinical composite (and the individual components: HF hospitalization, urgent HF visit, worsening HF event, cardiovascular death) will be summarized descriptively by treatment group, as described in Section 5.2.1.

A cumulative incidence plot, as described in Section 5.2.7, will be produced for the time to first occurrence of the clinical composite.

Time to first occurrence of the clinical composite (and the individual components: HF hospitalization, urgent HF visit, worsening HF event, cardiovascular death) will be analyzed using a Cox proportional hazards model, as described in Section 5.2.8. Note that for efficacy approaches 3 and 4, cohort will be included as a term in the statistical model.

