#### 7.2.1.1. Efficacy Endpoints

A subset, or all, of the following efficacy analyses will be produced: -

For KCCQ-23 CSS, 6MWD, NT-proBNP, hsCRP and eGFR, the descriptive summaries and main statistical analyses, described in Sections 6.1.1.1, 6.2.3, 6.3.12 and 6.3.13, will be performed. The statistical analyses will only include the 300 mg dose group and placebo. Additionally, Bayesian predictive probabilities will be calculated for the 300 mg dose group versus placebo, for end of study success based on the MMRM/ANCOVA results at Week 22 (and additionally Week 12 for eGFR). The predictive probabilities will be calculated using the method described by Grieve (1991), incorporating vague priors. Additionally, the categorical summaries will be produced for eGFR, as described in Section 6.3.13.

Additional subgroup analysis will be performed on KCCQ-23 CSS, 6MWD, NT-proBNP and eGFR, for screening CCI GDF-15 values (dichotomized using overall study median level) and cachexia presence/absence, as described in Section 6.4, excluding the descriptive summaries of absolute values. Summaries and analyses will only include the 300 mg dose group and placebo.

Note that eGFR summaries and analyses will be produced in separate outputs for the interim analysis.

For total vector magnitude and non-sedentary physical activity, the descriptive summaries described in Section 6.3.8, will be produced.

The number of participants with the composite HF outcome (cardiovascular death, hospitalization for HF or urgent HF visit) will be summarized and analyzed (using logistic regression), as described in Section 6.3.14.1. The statistical analyses will only include the 300 mg dose group and placebo. Additionally, Bayesian predictive probabilities will be calculated for the 300 mg dose group versus placebo, for end of study success based on the logistic regression results. The predictive probabilities will be calculated using the method described by Grieve (1991), incorporating vague priors.

The time to the first occurrence of the clinical composite will be summarized and analyzed as described in Section 6.3.14.2. The plot and statistical analysis will only include the 300 mg dose group and placebo.

Note that the investigator-reported clinical outcome events will be used for this interim analysis.

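### The logistic regression of the 22-week HF composite does not account for participants who leave or are censored event-free before Week 22

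*SAP*

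**What the plan says.** - **The model.** SAP 6.3.14.1 takes the number of participants with the composite HF outcome and says that it "over 22 weeks will also be analyzed using a logistic regression model (as described in Section 5.2.6), without any multiple imputation". SAP 5.2.6 adds that "Missing values (e.g. due to censoring) will not be imputed". It promises the odds in each arm and odds ratios against placebo, all with 90% CIs. This composite is the only endpoint that the SAP sends to Section 5.2.6.
- **The outcome definition.** SAP 3.3.14.1: "The composite HF outcome (cardiovascular death, hospitalization for HF or urgent HF visits) will be determined for each participant". It gives no rule for someone whose follow-up stops event-free before Week 22.
- **The analysis set.** SAP 6.3: "Unless otherwise stated these analyses will be performed on the censored analysis sets". Under SAP 4, that set treats as missing the data after discontinuation of study drug (last dose plus 31 days), after a prohibited procedure, or after a missed or incomplete dose. SAP 6.3.14 specifies adjudicated events and the efficacy approaches but names no other set.
- **Other analyses of the same composite.** SAP 6.3.14.2 plans a cumulative incidence plot (SAP 5.2.7, with dated censoring) and a Cox model (SAP 5.2.8).
- **The interim.** SAP 7.2.1.1 lists a Bayesian predictive probability for this composite, "for end of study success based on the logistic regression results".
- **Expected exit.** Protocol 9.5 sizes Cohort A "assuming a discontinuation rate of 15" percent.

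**The concern.** A yes/no outcome over 22 weeks is known only for participants who have an event or are followed event-free to Week 22. For someone who leaves event-free at Week 8 it is unknown. Two scorings fit the text. If every participant gets a value, the leaver becomes a non-event and the risk is understated. If the leaver's value is missing through censoring and is not imputed, the leaver drops out while leavers who had their event first stay in. That overstates the risk when exit is unrelated to later risk.

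The example code in SAP Appendix 4 starts from a finished response variable, so the programmer would have to choose. By contrast, SAP 3.2.2 and 5.3.4 state a rule for the KCCQ responder endpoints. At stake are the odds reported for each arm, the odds ratio if exit differs by arm, and the meaning of end-of-study success in the interim predictive probability. SAP 7.1 lets interim results inform futility, early success or sample size re-estimation.

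**Working it through.** **Inputs from the documents.** About 190 randomized per arm to 300 mg and to placebo in Cohort A, and 15% discontinuation with no difference by arm (Protocol 9.5); 22 weeks of follow-up. The plan's own figure reproduces: 190 × 0.85 = 161.5, against its approximately 161 evaluable per arm.

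**Assumptions.** The documents give no event rate for the composite. I take a true 22-week risk of 20% (range 5% to 30%), constant hazards, and exit unrelated to later risk. An exit of 15% means the probability of leaving by Week 22 if no event came first.

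**Formulas.** With time in units of 22 weeks, h = −ln(1 − risk) and g = −ln(1 − exit).
- Event seen: e = h/(h+g) × (1 − exp(−(h+g)))
- Event-free leaver: l = g/(h+g) × (1 − exp(−(h+g)))
- Event-free completer: c = exp(−(h+g))
- Leavers scored as non-events: risk = e, odds = e/(1 − e)
- Leavers dropped: risk = e/(e + c), odds = e/c

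**Equal exit of 15%, true risk 20%.** h = 0.2231, g = 0.1625, c = 0.80 × 0.85 = 0.680, e = 0.5786 × 0.320 = 0.1852, l = 0.1348.
- Scored as non-events: risk 18.5%, odds 0.1852/0.8148 = 0.227. The true odds are 0.20/0.80 = 0.250, so this is 9% too low.
- Dropped: risk 0.1852/0.8652 = 21.4%, odds 0.1852/0.680 = 0.272, 9% too high.
- At 30% exit the risks are 16.9% and 23.2%.
- With no drug effect the odds ratio is 1.00 under both scorings. For hazard ratios of 0.75 to 1.33 and placebo risks of 5% to 30%, it is off by at most about 1.0% (scored as non-events) or 0.2% (dropped).

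**Unequal exit, no drug effect, true risk 20%.**
- 300 mg, 20% exit: e = 0.180, c = 0.640. Odds are 0.180/0.820 = 0.2195 or 0.180/0.640 = 0.2813.
- Placebo, 10% exit: e = 0.1902, c = 0.720. Odds are 0.1902/0.8098 = 0.2349 or 0.1902/0.720 = 0.2642.
- Odds ratio: 0.2195/0.2349 = 0.935 (scored as non-events) or 0.2813/0.2642 = 1.065 (dropped).
- SE of the log odds ratio: √(2/(190 × 0.2 × 0.8)) = 0.256. The shifts are ln 0.935 = −0.068 and ln 1.065 = 0.063, about a quarter of an SE each way.
- Over true risks of 5% to 30% the odds ratios run from 0.942 to 0.928 and from 1.063 to 1.066. Reversing the exit rates reverses the directions.

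**Informative exit.** Let q be the leavers' risk of an event after leaving. The true risk is then e + lq, and the dropped-leaver risk minus the true risk equals l × (dropped-leaver risk − q). Independent exit at 20% risk and 15% exit implies q = (0.200 − 0.1852)/0.1348, about 11%. With the same e, l and c, if q exceeded 21.4%, both scorings would understate the risk.

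**The case against.** **The contradiction is inferred.** SAP 3.3.14.1 does not say that leavers count as non-events, and SAP 5.2.6 does not name them. One could read an event-recorded indicator as existing for everyone, with only missing covariates left unimputed. That is possible, but SAP 5.2.6 gives censoring as its example of why a value is missing and serves only this composite. The absence of a scoring rule stands.

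**The 15% is not shown to be lost outcome data.** Protocol 9.5 uses it to go from randomized to evaluable participants, and Protocol 7.1 and 7.2.1 keep participants in follow-up after they stop study drug. This stands: the number with unknown event status is not given. The censored-set default works the other way. A participant whose last dose is at Week 16 (Day 113) is censored at Day 113 + 31 = 144, before the Week 22 visit on Day 155, even if still followed.

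**The odds ratio is little affected.** A reader might infer that the two scorings always push the odds ratio in opposite directions. The documents do not support that. Their only exit rate is common to both arms and leaves the odds ratio practically unchanged; the 20%/10% split is an assumption.

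**The interim data are restricted already.** A reader might infer that the scoring choice distorts the Interim Analysis #1 data. SAP 7.2.1 limits its efficacy population to participants who complete the double-blind phase, so, read literally, leavers are out before any scoring arises. SAP 7.2.1.1 also commits only to some or all of its listed analyses. What remains is that the final logistic result being predicted has no defined denominator.

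**Better analyses are already planned.** The endpoint is tertiary, and the logistic model sits beside a Cox model and a cumulative incidence plot. That lowers the stakes and makes the repair cheap.

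**Conclusion.** The point holds in a limited form. The SAP gives no scoring rule for participants who leave or are censored event-free before Week 22, and its sections support two different denominators. Under constant hazards, exit unrelated to later risk, 20% true risk and 15% exit, the odds in each arm are about 9% too low or 9% too high, even when exit is the same in both arms. The odds ratio moves materially only if exit differs by arm: about 0.94 or 1.06 under the assumed 20%/10% split with no drug effect, small against its standard error. If leavers differ in later risk, the two errors need not be opposite. This warrants a change to the SAP, but it is not a threat to the primary analysis. Nor do the documents support going as far as requiring the logistic model to be deleted.

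**What to change.** 1. In SAP 6.3.14, make the Cox hazard ratio of 6.3.14.2 the main between-arm analysis of this composite. SAP 5.2.8 has no censoring rule of its own, so state one, for example by saying whether the dated rule in 5.2.7 applies.
2. Add the Week 22 difference in cumulative incidence with a 90% CI, so that an absolute risk is reported that uses partial follow-up.
3. In SAP 7.2.1.1, base the composite's predictive probability on the log hazard ratio and event counts.
4. If the logistic model is kept, label it supplementary and score all participants by one written rule: who is scored, over what window, and whether events after study-drug discontinuation count. Show the other scoring as a sensitivity analysis.

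The cost is SAP wording and minor reprogramming, with no new data. The hazard ratio and cumulative incidence still assume non-informative censoring, so they remove the scoring problem but not the effect of informative exit.
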